7.3. Study Discontinuation

All subjects, regardless of the completion or premature discontinuation, should perform the End of Study Visit according to the study flow-chart.

7.4. Screen and Baseline Failures

A subject is considered to be a baseline failure if the subject signs the informed consent but withdraws before the screening visit. All potential subjects who are screened for enrolment in this study will be listed on the Subject Screening Log/Identification List. Reasons for exclusion will be recorded for potential subjects who do not enter the study.

A subject who does not fulfil the randomization criteria will be considered as screen failure. All subject data should be entered in the eCRF including the screen failure data.

Based on the investigator evaluation and sponsor prior approval, a non-randomized subject can be re-screened. This re-screening procedure should be documented, the subject should consent again and a new unique and incremental subject Identification (ID) number be allocated.

8. ADVERSE EVENTS (AE) AND SERIOUS ADVERSE EVENTS (SAE)

The investigator is responsible for the detection and documentation of events meeting the criteria and definition of an AE or SAE. During the study, in case of a safety evaluation, the investigator or site staff will be responsible for reporting AEs and SAEs, as detailed in this section of the protocol.

During the screening period, only adverse event related to the screening procedures will be collected.

Any disease progression will not be reported in the eCRF as an adverse event, but will be documented in the efficacy section.

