8.1. Definition of an AE

Any untoward medical occurrence in a subject or clinical investigation subject administered a pharmaceutical product and which does not necessarily have to have a causal relationship with this treatment.

An AE can therefore be any unfavorable and unintended sign (including an abnormal laboratory finding), symptom, or disease (new or exacerbated) temporally associated with the use of a medicinal product, whether or not considered related to the medicinal product.

Note: The official definition also extends to AEs occurring in the placebo arm. Because of regulatory requirements, events occurring during pre-and post-treatment periods will also be designated as AEs. Therefore, reporting of such events, AEs and SAEs, will commence when the subject is enrolled into the study (date of signature of the informed consent) up until 4 weeks after the end of the treatment visits. The period after discontinuing study drug may be extended if there is a strong suspicion that the drug has not yet been eliminated.

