8.2. Definition of a SAE

A serious adverse event (experience) or reaction is any untoward medical occurrence that, at any dose:

a) Results in death

NOTE: Death is an outcome of an AE, and not an AE in itself. Event which led to death should be recorded with fatal outcome.

b) Is life-threatening

NOTE: The term 'life-threatening' in the definition of 'serious' refers to an event in which the subject was at risk of death at the time of the event. It does not refer to an event, which hypothetically might have caused death, if it were more severe.

c) Requires hospitalization or prolongation of existing hospitalization

NOTE: In general, hospitalization means that the subject has been detained (usually involving at least an overnight stay) at the hospital or emergency ward for observation and/or treatment that would not have been appropriate in the physician's office or out-subject setting. Complications that occur during hospitalization are AEs. If a complication prolongs hospitalization or fulfills any other serious criteria, the event is serious. When in doubt as to whether "hospitalization" occurred, or was necessary, the AE should be considered serious.

Hospitalization for elective treatment of a pre-existing condition that did not worsen after informed consent was given is not considered an AE.

d) Results in persistent or significant disability/incapacity,

NOTE: The term disability means a substantial disruption of a person's ability to conduct normal life functions. This definition is not intended to include experiences of relatively minor medical significance such as uncomplicated headache, nausea, vomiting, diarrhea, influenza, and accidental trauma (e.g. sprained ankle) which may interfere or prevent everyday life functions but do not constitute a substantial disruption.

e) Is a congenital anomaly/birth defect

f) Is another medically important condition: This refers to an AE that may not be immediately lifethreatening or results in death or hospitalization but may jeopardize the subject or may require intervention to prevent one of the outcomes listed above. Based on medical and scientific judgment this should usually be considered serious.

If there is any doubt about whether or not an AE is serious, the investigator should contact the sponsor.

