8.2.1. Events and/or Outcomes Not Qualifying as SAEs

Any hospitalization, or prolongation of hospitalization due to the circumstances listed below, will not be reported as SAE:

- planned medical/surgical procedure;
- planned medical/surgical admission (planned prior to entry into study, appropriate documentation required), for the disease under study;
- Administrative or social reasons (e.g. lack of housing, economic inadequacy, care-giver respite, family circumstances).

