8.3. Events or Outcomes Qualifying as AEs or SAEs

8.3.1. Clinical laboratory parameters

Abnormal laboratory findings (e.g., clinical chemistry, hematology) or other abnormal assessments (e.g. vital signs) that are judged by the investigator as **clinically significant** will be recorded as AEs or SAEs if they meet the definitions of sections 8.1 and 8.2 respectively. Clinically significant abnormal laboratory findings or other abnormal assessments that are detected during the study or are present at informed consent and significantly worsen during the study will be reported as AEs or SAEs. Clinically significant abnormal laboratory findings or other abnormal assessments that are associated with the disease being studied, and are present at the start of the study but do not worsen, will **not** be reported as AEs or SAEs. However, if these findings or assessments are judged by the investigator to be more severe than expected considering the subject's condition, then they may be reported as AEs or SAEs.

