8.4. Time Period, and Frequency of Detecting AEs and SAEs

All AEs and SAEs occurring from the time a subject consents to participate in the study until 4 weeks after he or she has completed or discontinued the investigational product must be recorded in the subject's eCRF.

Importantly, SAEs will have to be reported, either by email or by Fax, to SIMBEC ORION within 24 hours of awareness of an SAE.

SIMBEC ORION

[contact]

[contact]

Legislative guidance requires also reporting any **related** SAEs to be reported after the subject finished the study if the investigator becomes aware of them.

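### Protocol section 8 keeps disease progression out of the eCRF adverse event data with no exception for serious events, sections 8.1 to 8.4 require a serious UC event there, and SAP 11.4.1 does not settle it

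*Protocol*

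**What the plan says.** **The exclusion.** The opening text of Protocol section 8 says: "Any disease progression will not be reported in the eCRF as an adverse event, but will be documented in the efficacy section". Progression is not defined there, and serious events are not mentioned. The only definition of UC worsening is in section 7.2, as a reason for discontinuation, and section 8 does not refer to it.

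**The text that points the other way.**
- Section 8.1 includes in the AE definition any "symptom, or disease (new or exacerbated) temporally associated with the use of a medicinal product". UC is not excluded.
- Section 8.2 makes an event serious if it "Requires hospitalization or prolongation of existing hospitalization". Its note is narrow: "Hospitalization for elective treatment of a pre-existing condition that did not worsen after informed consent was given is not considered an AE".
- Section 8.2.1 exempts, among others, a "planned medical/surgical admission (planned prior to entry into study, appropriate documentation required), for the disease under study". An unplanned UC admission is not on the list.
- Section 8.3.1 says that clinically significant laboratory or other abnormal findings that "are present at informed consent and significantly worsen during the study will be reported as AEs or SAEs". Findings associated with the disease under study that "are present at the start of the study but do not worsen, will" not be reported.
- Section 8.4 covers "All AEs and SAEs occurring from the time a subject consents to participate in the study until 4 weeks after" the end of study drug and requires them all in the eCRF.

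**The SAP.** Section 11.4.1 decides whether an event is treatment-emergent from its timing and any increase in severity. It has no rule for UC worsening. Under SAP 9.1 and 9.2 the outputs are programmed from eCRF data, and the only external data sent to the statistics group are laboratory parameters.

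**The concern.** The primary objective is safety, and the primary endpoint is TEAE incidence on ABX464 against placebo, tested at a one-sided 10% level. Treatment-emergent SAEs are a secondary endpoint. Both counts depend on which events reach the eCRF as AEs, and for a serious UC event the protocol gives opposite instructions. Up to 20 sites in eight countries could each pick a different passage.

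The effect need not be equal in the two arms. If the drug works, UC worsening should be more common on placebo, so counting it would narrow an excess of TEAEs on ABX464.

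An event left out of the AE data may also have no other place in the tables. The SAP does not carry over the protocol's time-to-UC-worsening endpoint, and the shell of Table 14.1.2 has no UC-worsening category among the reasons for withdrawal.

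**Working it through.** **1. The passages applied to three cases**

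| Event on treatment | Section 8 opening text | Sections 8.1 to 8.4 |
|---|---|---|
| UC worsens, not serious | Not an AE in the eCRF | AE under 8.1 if it counts as an exacerbated disease |
| UC worsens, unplanned admission | Not an AE in the eCRF | SAE under 8.2, not exempt under 8.2.1, eCRF entry required by 8.4 |
| UC admission planned before entry | Not addressed | Not an SAE under 8.2.1 |

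The first row can be settled by treating section 8 as a specific exception. The second cannot. Section 8.2.1 deals with admissions for the disease under study and exempts only planned ones, a limit that would have little purpose if section 8 already removed every UC event.

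**2. The plan's own power figure**

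Inputs from Protocol 9.4: TEAE rates 10% (placebo) and 50% (ABX464), n = 10 and 20, one-sided alpha 0.10 (z = 1.2816), normal approximation.

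Power = Φ[(Δ − z·SE0)/SE1], with SE0 = √[p̄(1 − p̄)(1/10 + 1/20)] and SE1 = √[p0(1 − p0)/10 + p1(1 − p1)/20].

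- p̄ = (1 + 10)/30 = 0.3667; SE0 = √(0.2322 × 0.15) = 0.1866
- SE1 = √(0.0090 + 0.0125) = 0.1466
- Power = Φ[(0.40 − 0.2392)/0.1466] = Φ(1.097) = 86.4%

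This agrees with the stated 86%. There is no arithmetic error in the plan.

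**3. Sensitivity of the test to single subjects (illustration)**

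One placebo subject is 10 points of that arm's rate; one ABX464 subject is 5 points. The planned test is stratified, but the documents give no stratum sizes, so this uses the unstratified likelihood-ratio statistic G = 2ΣO·ln(O/E), with one-sided p = 1 − Φ(√G).

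For 10/20 against 1/10 the expected events are 7.333 and 3.667, and G = 2[1·ln(1/3.667) + 9·ln(9/6.333) + 10·ln(10/7.333) + 10·ln(10/12.667)] = 5.20.

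| ABX464 | Placebo | G | One-sided p |
|---|---|---|---|
| 10/20 | 1/10 | 5.20 | 0.011 |
| 10/20 | 2/10 | 2.65 | 0.052 |
| 10/20 | 3/10 | 1.11 | 0.146 |

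Two more placebo subjects with a TEAE move the result across the 10% level.

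**4. Power if UC worsening is counted (assumed rates)**

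Assumptions: 10% and 50% are the rates of other TEAEs, worsening is independent of them, and every site counts it. Combined rate = 1 − (1 − TEAE rate)(1 − worsening rate). For 10% in each arm: placebo 1 − 0.9 × 0.9 = 19%; ABX464 1 − 0.5 × 0.9 = 55%.

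| Worsening, placebo / ABX464 | TEAE, placebo / ABX464 | Difference (points) | Power |
|---|---|---|---|
| Not counted | 10% / 50% | 40 | 86% |
| 10% / 10% | 19% / 55% | 36 | 75% |
| 20% / 20% | 28% / 60% | 32 | 66% |
| 20% / 10% | 28% / 55% | 27 | 55% |
| 30% / 10% | 37% / 55% | 18 | 36% |

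Equal worsening in both arms also dilutes the difference, because fewer ABX464 subjects are free of another TEAE.

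**The case against.** The strongest reply is that section 8 is a deliberate, specific exception to a generic AE definition. It is categorical, it names another destination for the data, and section 7.2 lists UC worsening separately from adverse events as a reason to stop. Progression, exacerbation and the section 7.2 worsening are also different terms that the protocol does not equate. For non-serious worsening this reply stands: the exclusion is coherent, and SAP 11.4.1 would need no extra rule for events that never enter the AE data.

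A reader might infer that a UC flare can never be an adverse event, or that an emergency UC admission would escape 24-hour reporting and the DSMB. The documents support neither. Section 8 governs what is entered in the eCRF as an AE. SAEs travel separately, on SAE forms under sections 8.4 and 8.6, and nothing in 8.2 or 8.2.1 exempts an unplanned UC admission. What remains is the eCRF: an admission could be on an SAE form and yet be missing from the data behind the tables.

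Section 8.3.1 is supporting evidence only, since it concerns findings and assessments, not UC as a diagnosis. It is also fair to object that the rates in step 4 are invented and that section 9.4 does not say whether its 10% and 50% exclude UC worsening. Both points stand.

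Finally, SAP 3.1 planned recruitment to end in Q2 2018 and the SAP is dated 23 August 2018. If that timetable held, new protocol wording would come too late to change how events had been recorded.

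**Conclusion.** The conflict is real and is confined mainly to serious UC events. For these, section 8 excludes from the eCRF AE data what sections 8.2, 8.2.1 and 8.4 require there. Non-serious worsening is a clarity gap: exclusion may be intended, but the term is undefined and section 8.1 can be read the other way. No order of precedence is given, and the SAP does not choose.

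The effect on the primary test cannot be quantified from the documents. The p-value example shows only that, with 10 placebo subjects, two reclassifications can matter. The power range of 75% to 36% depends on assumed worsening rates, independence, uniform practice across sites and planned TEAE rates that leave UC worsening out. It is not an estimate of lost power, and it should not be read as the result of choosing one passage over another: the rates drive it as well.

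**What to change.** 1. Reconcile the opening text of section 8 with sections 8.1 to 8.3.1 and 8.4 in one rule that defines disease progression and says whether it counts as a TEAE.
2. State that a UC event meeting a section 8.2 seriousness criterion is reported as an SAE, entered in the eCRF, and counted in the TEAE and SAE tables.
3. Repeat the rule in SAP 11.4.1.
4. If a sensitivity row counting UC worsening is added to Table 14.3.1.1, state how worsening is derived from efficacy or discontinuation data, for example with the section 7.2 definition. It cannot come from AE terms, because excluded worsening would have none.
5. If recruitment has closed, check the SAE forms against the eCRF at the blind data review that SAP 9.4 already plans, so that serious UC events are treated alike before database lock.

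The cost is a few sentences in each document, a few more AE and SAE entries and a little more programming. None of this changes treatment or withdrawal rules.

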8.1. Definition of an AE

Any untoward medical occurrence in a subject or clinical investigation subject administered a pharmaceutical product and which does not necessarily have to have a causal relationship with this treatment.

An AE can therefore be any unfavorable and unintended sign (including an abnormal laboratory finding), symptom, or disease (new or exacerbated) temporally associated with the use of a medicinal product, whether or not considered related to the medicinal product.

Note: The official definition also extends to AEs occurring in the placebo arm. Because of regulatory requirements, events occurring during pre-and post-treatment periods will also be designated as AEs. Therefore, reporting of such events, AEs and SAEs, will commence when the subject is enrolled into the study (date of signature of the informed consent) up until 4 weeks after the end of the treatment visits. The period after discontinuing study drug may be extended if there is a strong suspicion that the drug has not yet been eliminated.

8.2. Definition of a SAE

A serious adverse event (experience) or reaction is any untoward medical occurrence that, at any dose:

a) Results in death

NOTE: Death is an outcome of an AE, and not an AE in itself. Event which led to death should be recorded with fatal outcome.

b) Is life-threatening

NOTE: The term 'life-threatening' in the definition of 'serious' refers to an event in which the subject was at risk of death at the time of the event. It does not refer to an event, which hypothetically might have caused death, if it were more severe.

c) Requires hospitalization or prolongation of existing hospitalization

NOTE: In general, hospitalization means that the subject has been detained (usually involving at least an overnight stay) at the hospital or emergency ward for observation and/or treatment that would not have been appropriate in the physician's office or out-subject setting. Complications that occur during hospitalization are AEs. If a complication prolongs hospitalization or fulfills any other serious criteria, the event is serious. When in doubt as to whether "hospitalization" occurred, or was necessary, the AE should be considered serious.

Hospitalization for elective treatment of a pre-existing condition that did not worsen after informed consent was given is not considered an AE.

d) Results in persistent or significant disability/incapacity,

NOTE: The term disability means a substantial disruption of a person's ability to conduct normal life functions. This definition is not intended to include experiences of relatively minor medical significance such as uncomplicated headache, nausea, vomiting, diarrhea, influenza, and accidental trauma (e.g. sprained ankle) which may interfere or prevent everyday life functions but do not constitute a substantial disruption.

e) Is a congenital anomaly/birth defect

f) Is another medically important condition: This refers to an AE that may not be immediately lifethreatening or results in death or hospitalization but may jeopardize the subject or may require intervention to prevent one of the outcomes listed above. Based on medical and scientific judgment this should usually be considered serious.

If there is any doubt about whether or not an AE is serious, the investigator should contact the sponsor.

8.2.1. Events and/or Outcomes Not Qualifying as SAEs

Any hospitalization, or prolongation of hospitalization due to the circumstances listed below, will not be reported as SAE:

- planned medical/surgical procedure;
- planned medical/surgical admission (planned prior to entry into study, appropriate documentation required), for the disease under study;
- Administrative or social reasons (e.g. lack of housing, economic inadequacy, care-giver respite, family circumstances).

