9.4. Determination of Sample Size

The primary efficacy endpoint is the rate of subjects responding to treatment. This response rate will be compared in subjects who received ABX464 or placebo by likelihood ratio chi-square test. For the sample size assessment, the following assumptions will be made:

- Response rate (ABX464): 0.6
- Response rate (placebo): 0.2

According to literature the response rate for ABX464 treated subjects is expected to be between 50% and 75% while that in the placebo group is assumed to be approximately 10% to 20% (Gemini 1 study - N Engl J Med 2013; 369:699-710 August 22, 2013).

- Type 1 error: 10% one-sided
- Group allocation rate (ABX464 / placebo): 2:1

If the above assumptions and definitions hold true with a sample size of 30 subjects receiving ABX 464 or placebo in a ratio of 2:1 the study has 81% power to show a difference in response rate between the study groups. To gain more clinical experience with ABX464 in this indication a 2:1 randomization ratio was chosen despite the inevitable loss of power. The actual loss of power with the above assumptions is 4%. Power was computed using the normal approximation method.

Subjects who terminates the study prematurely will be considered failures therefore no adjustment for dropouts is needed.

Primary safety endpoint is the rate of all treatment emergent adverse experiences. The above sample size is sufficient to detect an increase in general treatment emergent adverse experience rate from 10% to 50% with 86% power by likelihood ratio chi-square test on a 10%, one-sided significance level.

If approximately 20 subjects receive ABX464 the study has 88% chance to detect at least 1 specific treatment emergent AE if the underlying rate of occurrence is 1:10.

When the underlying rate of occurrence is around 1:20 the sample size of 20 subjects is sufficient to observe at least 1 such an event with a probability of 64% in the active treatment group.

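### Protocol 8.2.1 exempts admissions for planned procedures from SAE reporting without a before-entry condition, which conflicts with 8.2(c) and can leave a serious event unreported

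*Protocol*

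**What the plan says.** Protocol section 8.2(c) makes an untoward event serious if it "Requires hospitalization or prolongation of existing hospitalization". Its notes then set one elective exclusion: "Hospitalization for elective treatment of a pre-existing condition that did not worsen after informed consent was given is not considered an AE". They also deal with complications: "If a complication prolongs hospitalization or fulfills any other serious criteria, the event is serious".

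Section 8.2.1 follows directly and lists exemptions under the rule "Any hospitalization, or prolongation of hospitalization due to the circumstances listed below, will not be reported as SAE". There are three:

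- The first is "planned medical/surgical procedure", with nothing on when it was planned, how it is documented or what it is for.
- The second is "planned medical/surgical admission (planned prior to entry into study, appropriate documentation required), for the disease under study".
- The third covers administrative and social reasons.

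Neither section refers to the other, and neither is said to take precedence.

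Protocol section 2.4 lists treatment-emergent SAEs as a secondary endpoint. SAP section 11.4.1 counts a TEAE as serious when the recorded seriousness field is yes or is missing.

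**The concern.** The planning-date and documentation condition sits inside the second exemption only. A site can therefore take the first one at face value. If an event begins on study drug and the subject is later admitted for a scheduled procedure to investigate or treat it, that admission is for a planned procedure and need not be reported as an SAE. Under 8.2(c) the same admission would make the event serious.

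The effect would be felt in two places:

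- **Expedited reporting.** The 24-hour report (protocol 8.4 and 8.6) is triggered only by an SAE, and the safety reports to investigators in 8.7 require an event to be serious as well as unexpected and associated with the product. A report missed during the trial cannot be made on time afterwards.
- **The analysis.** A seriousness field recorded as no keeps the event out of the SAE row of SAP Table 14.3.1.1 and out of the serious and serious drug-related TEAE tables. The SAP specifies no later check of that field for planned admissions.

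**Working it through.** The point rests on wording, so the check is to run cases through both sections.

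- **Procedure planned before entry, pre-existing condition stable since consent.** 8.2(c): not an AE. First exemption in 8.2.1: not an SAE. The sections agree.
- **Procedure planned before entry, non-UC pre-existing condition worsened since consent.** 8.2(c): the elective exclusion no longer applies, so the admission can make the event serious. First exemption: not reported. The sections conflict.
- **Procedure scheduled after entry because of a new or worsened on-treatment event, no other seriousness criterion met.** 8.2(c): serious through hospitalisation. First exemption: not reported. The sections conflict, and this is the main exposed case.
- **As above, but the event also meets 8.2(a), (b), (d), (e) or (f).** The event is serious on that other ground, whatever is decided about the admission.
- **Complication that prolongs a planned stay.** 8.2(c) says outright that this is serious.
- **Admission for UC progression.** Section 8 keeps disease progression out of AE recording altogether, so 8.2.1 is not what removes it.

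The conflict is thus confined to the second and third cases.

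**Size per subject.** The planned arms are 20 on ABX464 and 10 on placebo (protocol 3.1.1). One subject whose SAE is not reported moves the observed rate by 1/20 = 5 percentage points on ABX464 or 1/10 = 10 percentage points on placebo. The documents give neither an SAE rate nor a share of admissions that are for procedures scheduled after entry, so no expected number can be derived.

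**Section 9.4 figures.** The chance of at least one event among 20 subjects is 1 − (1 − p)^20.

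- p = 0.10: 1 − 0.90^20 = 87.8% (stated 88%).
- p = 0.05: 1 − 0.95^20 = 64.2% (stated 64%).

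Both reproduce. In both, p is the rate of a specific treatment-emergent AE, serious or not. Section 8.2.1 removes a hospitalisation from SAE reporting and leaves the underlying event to be recorded as an AE under 8.4. So p does not change, and neither do these figures.

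**Room for different readings.** Section 4.1 allows up to 20 sites in eight countries for 30 subjects, which is 30/20 = 1.5 subjects per site if all open and recruit evenly. With so few subjects at each site, whether an event is reported could depend on which section that site follows.

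**The case against.** The case against giving this much weight is substantial, and most of it stands.

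- Section 8.2 leans towards reporting. It treats doubt about whether a hospitalisation occurred or was needed as a reason to call the event serious, sends doubts about seriousness to the sponsor, and offers the medically important route in 8.2(f). A careful investigator may well report the event despite the first exemption.
- 8.2(c) does not make every other admission serious. There must still be an untoward medical occurrence behind it.
- The exposed group is small. It needs a non-UC event in the 8 weeks of treatment or the 4 weeks after, a scheduled inpatient procedure, no other seriousness criterion, and a site that puts 8.2.1 above 8.2(c). Subjects with planned bowel surgery or at imminent risk of colectomy are already excluded (4.2.2).
- Other safety information survives. Grade 3 or 4 TEAEs and TEAEs leading to discontinuation have their own tables, the DLT rule in 3.1.3 uses grade and relatedness rather than seriousness, and the DSMB reviews the overall safety profile.

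These points limit how often the conflict would matter. They do not say which section governs when it arises.

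A reader might also infer that the 64% and 88% in section 9.4 should be scaled down by whatever share of events is exempted. The documents do not support that, because those figures concern TEAEs of any seriousness, which are still recorded.

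**Conclusion.** The point holds as an internal inconsistency. The first exemption in 8.2.1 lacks the condition carried by the second, conflicts with 8.2(c), and no text settles the matter. An SAE that rests only on an admission scheduled after entry could go unreported at a site that reads the exemption literally. Each such subject is worth 5 points of 20 on ABX464 or 10 points of 10 on placebo, assuming the planned arm sizes and that the event meets no other seriousness criterion.

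Two stronger readings should be avoided. One is that these admissions necessarily leave the SAE count: the loss is possible, not certain, because 8.2(c), 8.2(f) and the rule for doubtful cases can each still bring the event in. The other is that the trial's primary safety result is biased. The primary endpoint is all TEAEs (protocol 2.3, SAP 4.1), and the planned safety test is on the TEAE rate. Both are unaffected. What is exposed is expedited reporting, the secondary SAE endpoint and the descriptive serious-TEAE tables.

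**What to change.** Make two small changes in section 8.2.1:

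1. Apply to the first exemption the before-entry and documentation condition that the second already carries. That condition comes from 8.2.1 itself. Section 8.2 has no planning-date or documentation requirement.
2. State that 8.2.1 is subject to 8.2(c), so that an admission for a procedure scheduled after consent because of a new or worsened condition is assessed for seriousness under 8.2. This is needed as well as the first change, because a procedure planned before entry may be for a condition that has since worsened.

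The second exemption counts from study entry and 8.2(c) from informed consent, so the revised text should name one reference date. The same wording should go into the SAE form instructions. The cost is a line or two of protocol text and possibly a few more SAE reports. The analysis plan and sample size do not change.
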